We hypothesize that greater improvement in PROs will be noted with the SAM clinic intervention compared to usual care.

SA 3. To examine the impact of the SAM Clinic on changes in barriers to PAP adherence compared to usual care from baseline contact to 3 months in those with moderate to severe OSA with suboptimal PAP adherence.

We hypothesize that the SAM Clinic intervention will be able to address PAP barriers more effectively

compared to usual care.

PRELIMINARY DATA:
A. Impact of the SAM
Clinic on PROs and
PAP barriers

Table 1: PRO Changes following SAM treatment in OSA patients								
	ESS		FSS					
	Change (95% CI)	p-value	Change (95% CI)	p-value				
Post- SAM	-1.52 (95% CI -2.10, -0.93)	<0.001	-2.88 (95% CI -4.73, -1.03)	<0.001				

(presented at SLEEP 2018)

A.1 Changes in PROs: We analyzed changes in the Epworth Sleepiness Scale (ESS) and the Fatigue Severity Scale (FSS) by capitalizing on the integration of the CC Knowledge Program (electronic PRO data collection platform, described in more detail below) with the electronic medical record, before and after SAM Clinic (180 days), in 235 patients. Table 1 demonstrates statistically significant improvements in ESS and FSS, suggesting additional benefits of the SAM Clinic on patients already on PAP therapy.

A.2 Changes in Barriers: We examined the impact of the SAM Clinic on PAP barriers in 21 patients and noted complete resolution of air leak (n=7), mask claustrophobia (n=6), and aerophagia (n=3). Mask-fitting issues were resolved in 10/11 patients, pressure intolerance was resolved in 9/10, and mouth dryness was resolved in 10/14 patients (p<0.05 for all except aerophagia).

[figure not shown]
B. Data Highlighting the Impact of PAP on PROs in Sleep-Disordered Breathing (SDB)

[figure not shown]
B.1 Changes in PROs with PAP in patients with hypertension and resistant hypertension in a clinical population of SDB: We examined improvements in PROs in 894 patients with PAP treatment for SDB in the hypertension and resistant hypertension population, which is an understudied area. Table 2 demonstrates the improvement

Table 2: PRO Changes following PAP treatment in SDB									
	Epworth Sleepines	ss Score	Patient Health Question	onnaire-9	Fatigue Severity Scale				
	Change (95% CI)	p-value	Change (95% CI)	p-value	Change (95% CI)	p-value			
Post- PAP	-2.09 (-2.37, -1.82)	<0.001	-1.91 (-2.25, -1.56)	<0.001	-4.06 (-4.89, -3.22)	<0.001			

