Eligibility criteria: Inclusion Criteria: 1) ≥18 years old 2) Moderate to severe OSA (apnea hypopnea index (AHI), respiratory disturbance index (RDI), Respiratory Event Index (REI)≥5 events/hr) on polysomnogram (PSG) or home sleep apnea testing (HSAT) 3) Followed by non-sleep and sleep providers for OSA 4) New PAP set up < 1 month 5) Sub-optimal PAP adherence by objective PAP adherence data (≤70 % usage and ≤4 hours of average PAP usage) Exclusion criteria: 1) Central sleep apnea (≥50% apneas are central) and/or presence of Cheyne-Stokes breathing 2) Pregnant women 3) Patients on supplemental oxygen 4) Patients not able to attend SAM clinic 5) Inability to provide informed consent

Randomization: Patients will be randomized 1:1 to SAM clinic/sleep hygiene or usual care/sleep hygiene (care by non-sleep providers) using a blocked randomization that stratifies patients based on OSA severity (AHI, RDI, REI 5-14.9, 15-29.9 vs. AHI, RDI, REI >30+). Random assignments to the three arms will be made

with the use of a randomization database in REDcap.

Study Protocol: All data from PAP devices set up by CCDME will be downloaded via wireless communication or smartcard. PAP adherence will be monitored by the research coordinator before randomization (randomized to SAM Clinic or usual care with their provider) and after 1 and 3 month of either intervention. A sample size of approximately 83 subjects is estimated in each group over a period of 2 years (total n=166). SAM clinic appointment will be offered within 1-2 weeks of patient consent and randomization into that group. Both groups will be provided with PAP barriers questionnaires which will be administered in "yes/no" format focused upon specific mask issues (air leak, irritation, fitting problems, type of mask) and other issues (nasal congestion, claustrophobia etc.) and the same questionnaires will be instituted in both the groups at the 1- and 3-month follow-up through the email using redcap platform. See Figure 2 for the flow diagram of the study.

[figure not shown]
[figure not shown]

Figure 2: Flow Diagram of Study

Sleep Hygiene Education: A research coordinator will provide both the arms with sleep hygiene education material at baseline that entails regularization of sleep wake schedule, stimulus control education, adequate amount of sleep and comfortable environment conducive to sleep (by mail).

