Data Analysis Plan: Patients will be randomized 1:1 to the two treatment groups using a blocked randomization that stratifies patients based on OSA severity (AHI, RDI, REI 5-15 vs.15-30, 30+). Blocks will be of random size blinded from study investigators. Only the intent-to-treat population will be included in primary analyses, while secondary analyses will be performed in the per-protocol population defined by participation in the SAM Clinic for the treated group versus usual care patients. Linear and non-linear mixed effect models will be used to compare groups for changes in PAP adherence (primary endpoint), PROs, and barriers over time. In these models, group by time interactions will be used to evaluate trend differences between groups, and mean differences primarily at 3 months and secondarily at 1 month. The use of mixed effect models will account for loss to follow-up under the assumption that such dropout is missing at random, though this assumption will be evaluated graphically. If data are missing not at random, pattern mixture models will be further explored to evaluate group differences. Analyses will be performed assuming an overall significance level of 0.05, and comparisons of mean differences at 1 and 3 months will each use a 0.05 significance level. Statistical support will be provided by a biostatistician within the Cleveland Clinic Department of Quantitative Health Sciences for this project.

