Sample Size: Sample size calculations were performed based on detecting mean differences in PAP adherence at 1 and 3 months. In this study, patients undergoing motivational enhancement (ME) showed an average PAP adherence of 264 minutes (SD: 174) as compared to average PAP adherence of 198 (SD: 168) among those without ME. Given the overall paucity of data addressing PAP adherence in a group setting-we utilized this data from RCT with ME given the similarities in approach. If we assume a similar effect size, and assume that average adherence will be log-normally distributed with a coefficient of variation of 0.65, there will be 80% power to detect an increase of 33% in the mean average nightly PAP adherence with 67 patients per group. Allowing for non-participation and non-compliance rates of 10% in each group, a total of 83 patients per group will be enrolled, the adjustment described by Lachin. This sample size will also provide similar power to detect moderate effect size differences between study groups on PROs, even allowing for dropout on these measures of up to 20% on these measures. Power calculations were performed using SAS software (version 9.4; Cary, NC) and assumed use of a two-sided test with significance levels of 0.05.

Limitations/Pitfalls and Alternative Strategies: Since this is a comparative study comparing the effectiveness of SAM clinic to usual standard of care by providers, there are inherent limitations to such a design. There is a possibility of cross over for the patients. We have accounted for possible cross-contamination in the statistical design by increasing the sample size. Patient without email access will be sent paper format of questionnaire. If recruitment become a challenge, will target recruitment efforts in primary care clinics. This study may not be able to shed the light on effectiveness specific mechanisms of SAM clinic intervention e.g. group component vs sleep provider interaction or more. Further research will be needed to investigate it.

Adverse Event Reporting: Reporting of adverse events will follow standard reporting guidelines. Each event will be classified according to its severity, whether it was expected or unexpected, and its likelihood of relatedness to the study and reviewed by the study medical monitor, [name].

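### The overall 0.05 level covers the primary test at 3 months but not Hypotheses 2 and 3, which have no lead measure, testing order or adjustment

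*Combined protocol and SAP*

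**What the plan says.** The Data Analysis Plan contains one statement on error control: "Analyses will be performed assuming an overall significance level of 0.05". The sentence goes on to say that "comparisons of mean differences at 1 and 3 months will each use a 0.05 significance level". The mixed models are to "compare groups for changes in PAP adherence (primary endpoint), PROs, and barriers over time", so the same level is used for all three kinds of outcome. Visits are ranked: the models estimate "mean differences primarily at 3 months and secondarily at 1 month". PAP adherence is the only outcome labelled primary.

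Hypothesis 2 concerns the PROs as a group: "We hypothesize that greater improvement in PROs will be noted with the SAM clinic intervention compared to usual care". SA 2 names three domains (sleepiness, quality of life, depressive symptoms). The PRO Questionnaires section lists six instruments: ESS, PHQ-9 and PROMIS Global Health, Sleep Related Impairment, Fatigue and Anxiety. Hypothesis 3 likewise concerns barriers as a group. The Study Protocol section describes a yes/no "format focused upon specific mask issues (air leak, irritation, fitting problems, type of mask"), then adds nasal congestion and claustrophobia and leaves the list open.

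No section names a lead PRO, a barrier summary, an order of testing or an adjustment. The Sample Size section states power for PAP adherence and for a moderate PRO difference, but none for barriers.

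**The concern.** An overall level is a promise about a set of tests. Here it equals the level of each test in the set, and nothing ties the tests together. Hypotheses 2 and 3 are each a single directional claim, but no rule says which result would confirm them, so one significant questionnaire or barrier could be presented as confirmation. The Dissemination Plan foresees separate manuscripts on PROs and on barriers, so each hypothesis will carry its own headline. Readers told that the overall level was 0.05 would give those headlines more weight than they have earned.

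**Working it through.** **1. The plan's own figures.** Inputs from the Sample Size section: 264 vs 198 minutes, log-normal, CV 0.65, 80% power, and a "assumed use of a two-sided test with significance levels of 0.05".
- Log-scale SD = √ln(1 + 0.65²) = 0.594; log ratio = ln(264/198) = 0.288.
- n per group = 2 × [(1.960 + 0.842) × 0.594 / 0.288]² = 67 (with unrounded values), as stated.
- Inflation: 67 / (1 − 0.10)² = 82.7, so 83, as stated.
- PROs: 20% dropout from 83 leaves 66 per group. Taking a moderate effect as 0.5 SD (an assumption), power = Φ(0.5 × √(66/2) − 1.960) = Φ(0.912) = 81.9%. This agrees with the plan's claim of similar power, but for one PRO tested at 0.05.

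The sample size is not at fault.

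**2. One measure, two visits.** If either visit could support a claim, the chance of at least one false positive is 1 − 0.95² = 9.75% with independent tests. With between-visit correlation of 0.3 to 0.9 (assumed) it is 9.5% to 7%. The ranking of 3 months over 1 month removes this problem for PAP adherence, provided 3 months alone decides.

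**3. Hypothesis 2 at 3 months.** Each PRO is tested two-sided at 0.05, there is no true effect, and the test statistics are multivariate normal with equal correlation. The documents give no correlations, so a range is shown.

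| PROs counted | Independent | 0.3 | 0.5 | 0.7 |
|---|---|---|---|---|
| Six questionnaires | 1 − 0.95⁶ = 26.5% | 24% | 21% | 16% |
| Three SA 2 domains, one measure each | 1 − 0.95³ = 14.3% | 14% | 13% | 11% |

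If 1 month also counts, the figure for six questionnaires is 27-39% (instrument correlation 0.7 to 0.3, between-visit correlation 0.6, all assumed). These figures count significance in either direction, to match a two-sided 0.05.

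**4. Hypothesis 3.** Six barrier topics are named. If each were tested separately at 3 months, the arithmetic is that of the first row: 26.5% if independent and 16-24% at correlation 0.7 to 0.3. This is conditional, because the plan does not say that items are tested separately.

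**5. Barrier power.** The only barrier data are uncontrolled: Preliminary Data A.2 reports 21 patients, with "complete resolution of air leak (n=7), mask claustrophobia (n=6), and aerophagia (n=3"), mask fit resolved in 10/11, pressure intolerance in 9/10 and mouth dryness in 10/14. Take those counts over 21 as baseline prevalence, the pilot resolution rates for SAM, 66 per group, and a two-proportion normal test at 0.05. The usual-care resolution rate must be assumed.
- Example, air leak with half resolved under usual care: 7/21 × 0.5 = 16.7% remaining vs about 0%, giving 94% power.
- The other items, same assumption: mask fit 93%, claustrophobia 89%, pressure intolerance 89%, aerophagia 58%, mouth dryness 46%.
- If usual care resolves three quarters, no item exceeds 66%.

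Single-item power therefore turns on a rate that the documents do not give.

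**The case against.** The best defence is that PAP adherence is the sole primary endpoint and that the secondary aims need no family-wise control. The first part stands: nothing here inflates the 3-month adherence test, and a reader who inferred that the trial's main result is compromised would be wrong. The second would also stand if the plan called the secondary tests unadjusted or exploratory. It does not; it gives them directional hypotheses and claims an overall level.

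It can also be said that the sentence means the level of each model's overall test, followed by its visit contrasts. That reading is possible, since the 0.05 per visit is openly declared. But it makes 0.05 a per-model level with no bearing on the set of outcomes, and the text would need to say so.

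Six questionnaires may be too many for Hypothesis 2, since SA 2 names only three domains. That is fair, and the smaller count is shown above; it still gives more than twice 0.05.

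A reader might go further and infer that Aim 3 uses item-by-item tests with little power. The documents do not support this. The plan says only that barriers are compared over time; item-wise reporting appears only in the pilot data. At the pilot resolution rates, four of six items reach 89% or more even if usual care resolves half. Those rates may be optimistic, being uncontrolled and based on as few as 3 patients. In addition, aerophagia, mouth dryness and pressure intolerance are not among the barriers the Study Protocol section names. What can be said is that neither a barrier outcome nor its power is stated.

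**Conclusion.** The concern holds in limited form. The overall 0.05 is correct for PAP adherence at 3 months. It does not hold for Hypothesis 2 if any one PRO can confirm it: the false-positive chance at 3 months is 16-24% with six questionnaires or 11-14% with three, assuming equal correlation of 0.7 to 0.3. Hypothesis 3 is exposed in the same way only if items are tested one by one. The defect there is an undefined outcome with no stated power, not a demonstrated lack of power. This should be corrected before outcomes are compared by arm, but it does not threaten the primary analysis or the sample size.

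**What to change.** In the Data Analysis Plan:

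- Limit the overall 0.05 statement to PAP adherence at 3 months.
- For Aim 2, list the instruments that bear on Hypothesis 2 and name one lead PRO at 3 months, tested at 0.05. The choice is the sponsor's; ESS is one example. Holm-adjust the others or label them exploratory. To hold 0.05 within the aim, the Holm step should be reached only if the lead PRO is significant.
- For Aim 3, name one barrier summary at 3 months, for example the number of barriers per patient, with single items descriptive. State its power and the assumed usual-care rate.
- Label the 1-month tests as secondary and unadjusted.

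The cost is a few sentences and no extra patients or data. One lead PRO keeps 81.9% power. Bonferroni over all six (0.05/6) would instead give Φ(2.872 − 2.638) = 59.3%, so naming a lead is the cheaper route. The price is that other PROs and single barriers carry less weight.

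A count can also dilute an effect confined to a few barriers. With pilot prevalences, 66 per group and assumed resolution of 50% vs 70%, simulated power for the count is 61-88% if every barrier improves. It is 17-29% if only fit, leak and claustrophobia do (latent correlation between items 0.4 to 0). The sponsor should weigh this when choosing the summary.

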The Sleep Apnea Management Clinic (SAM) is a novel group clinic created and embedded in the Cleveland Clinic (CC) System to address challenges in positive airway pressure (PAP) management by promoting adherence via providing access to problem-solving of PAP therapy issues. This innovative and interactive format allows patients with common problems and needs to have direct access to sleep medicine providers, sleep nurse practitioners, sleep nurses and/or durable medical equipment (DME) representatives all in one room in order to receive the most efficient service. While there are limited data focused on examining group clinics for PAP education, there are scant data that have assessed PAP adherence and its barriers in a group setting. Our team has played an integral role in the design, development, and establishment of the SAM Clinic initiative and has extensive experience in its management and operations. We propose a randomized controlled trial, involving 83 patients in SAM clinic and 83 patients in usual care and compare PAP adherence, patient reported outcomes and PAP barriers. Expected results will be of high impact given ability to identify and inform future treatment approaches for management of OSA with PAP and identify key outcomes for clinical trials. In doing so, this line of investigation will likely have a significant clinical impact to enhance PAP adherence and ameliorate adverse clinical outcomes associated with OSA patient populations across systems of care.

Specific Aims

SA 1. To examine the impact of the sleep apnea management (SAM) group-based intervention on Positive Airway Pressure (PAP) adherence (primary outcome) compared to a patient group managed by physicians (patients who follow usual care and are receptive to the SAM Clinic but do not participate in a SAM group) on changes from baseline to 1 and 3 months in those with moderate to severe OSA with suboptimal PAP adherence.

Hypothesis 1: We hypothesize that the SAM clinic intervention will result in improved PAP adherence versus usual care.

SA 2. To examine and compare changes in patient reported outcomes (PROs, i.e. daytime sleepiness, quality of life measures, and depressive symptoms) between the SAM Clinic and the usual care arms from baseline to 1 and 3 months in those with moderate to severe OSA with suboptimal PAP adherence. To examine the correlation between changes in PROs to changes in PAP adherence at each time point (secondary analyses).

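### Does testing adherence at both 1 and 3 months at 0.05 leave the error rate for Aim 1 uncontrolled?

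*Combined protocol and SAP*

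**What the plan says.** The Data Analysis Plan names change in PAP adherence as the primary endpoint and compares the arms with mixed-effects models. In those models "group by time interactions will be used to evaluate trend differences between groups", and the arms are also compared on "mean differences primarily at 3 months and secondarily at 1 month". On significance levels, a single sentence sets an "overall significance level of 0.05, and comparisons of mean differences at 1 and 3 months will each use a 0.05 significance level".

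Other sections do not repeat the ranking. Under Specific Aims, Aim 1 compares the arms "on changes from baseline to 1 and 3 months", and Hypothesis 1 gives no time point: "We hypothesize that the SAM clinic intervention will result in improved PAP adherence versus usual care". The Sample Size section begins: "Sample size calculations were performed based on detecting mean differences in PAP adherence at 1 and 3 months". It goes on to assume two-sided tests at 0.05.

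**The concern.** An overall level of 0.05 and two comparisons at 0.05 each cannot both hold if either comparison may support the claim. Several rules would reconcile them: 3 months alone decides, a fixed testing order, a joint test first, or significance required at both times. The plan names none of these in words. Aim 1, Hypothesis 1 and the Sample Size section do not rank the time points, and the group-by-time interaction could be taken as a third route to a positive finding.

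The awkward outcome is a significant difference at 1 month that has faded by 3 months, which is plausible for an intervention offered soon after randomization. If the plan were truly silent on that outcome, the team could decide whether Aim 1 had been met after seeing the data, and the true error could approach 10%.

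**Working it through.** **1. The plan's own sample size.** Inputs from the Sample Size section: means of 264 and 198 minutes, coefficient of variation 0.65, log-normal data, 80% power, two-sided 0.05.

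- Log-scale SD = sqrt(ln(1 + 0.65²)) = 0.594.
- Log ratio = ln(264/198) = ln(1.333) = 0.288.
- n per group = 2 × [0.594 × (1.960 + 0.842) / 0.288]² = 66.8 with unrounded inputs, so 67. This matches the plan.
- Inflation: 67 / (1 − 0.10)² = 67 / 0.81 = 82.7, so 83. This also matches.
- Power at 67 per group is 80.1% by the normal approximation (79.4% if the ratio is taken as 1.33).

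The stated size therefore fits one two-sided test at the full 0.05. No alpha was split between the time points.

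**2. Error for Aim 1 under each reading, with no true effect.** The documents give no correlation between the 1-month and 3-month test statistics, so a range is assumed. The same patients are measured twice, which makes a correlation of 0 unlikely.

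- 3 months decides: 5.0% whatever the correlation.
- Either time point may decide: P(|Z₁| > 1.96 or |Z₃| > 1.96) under a bivariate normal. At correlation 0 this is 1 − 0.95² = 9.75%.

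| Assumed correlation | Either time point significant | 1 month significant, 3 months not (previous column − 5%) |
|---|---|---|
| 0 | 9.75% | 4.8% |
| 0.5 | 9.1% | 4.1% |
| 0.7 | 8.4% | 3.4% |
| 0.9 | 7.0% | 2.0% |
| 0.95 | 6.5% | 1.5% |

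The last column is the chance, under no effect, of the outcome said to be unresolved. If a trend test could count as well, simulation puts the total anywhere from 6.8% to 12.2%, depending on the form of test and the correlation. No section makes a trend result decisive.

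**3. Which reading the text supports.** The Data Analysis Plan attaches *primary* to adherence among the endpoints and *primarily* to 3 months among the times. Together these identify one primary comparison, adherence at 3 months. Aim 1 and the Sample Size section list the times without ranking them, but neither says that either time alone is enough. The analysis section is the more specific text on how the comparisons are to be used. So 1 month positive with 3 months negative is a failed primary comparison with a positive secondary one. Testing a secondary comparison at 0.05 adds nothing to the error of the primary claim.

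**4. What a change would gain or cost.** Stating that 3 months alone decides leaves the error at 5.0%, power at about 80%, and 67 inflated to 83 per group. Splitting alpha at 0.025 each would cut power at 67 per group to 71.3% (70.5% at ratio 1.33). Restoring 80% would need 81 to 83 per group before inflation, or 100 to 103 after dividing by 0.81, to guard against a reading the text does not favour.

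**The case for a change.** The strongest contrary case is that a ranking orders emphasis without saying what counts as success. The ranking sits in a sentence about models that also cover patient-reported outcomes and barriers. It is not repeated in Aim 1, Hypothesis 1 or the Sample Size section, so a reader who starts there could treat either time point as confirming the aim. An explicit rule would take two or three sentences, and the time to write it is before the data are seen.

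Part of this stands. No sentence says that 3 months alone decides Aim 1, overall is undefined, and the role of the interaction in that decision is unstated. But overall need not mean familywise: the sentence covers analyses in general, the plan never claims familywise control, and the Sample Size section also speaks of significance levels in the plural. Read as a default level for each test, it does not conflict with 0.05 at each time. It also plausibly supplies the level for the interaction test. The wish for explicit wording is fair, but it falls short of showing that the plan would mislead.

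**Conclusion.** No change follows. The plan's ranking already makes the 3-month adherence difference the primary comparison, with a two-sided error of 5.0% and about 80% power at 67 evaluable patients per group. The figures of 6.5% to 9.8% need a 1-month result alone to count as success, against the word secondarily, and they rest on assumed correlations of 0.95 to 0. The figures up to 12.2% also need a decisive trend test that the plan does not contain.

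The gap is one of drafting, and a competent analyst would fill it as the text points: report the 3-month difference as the test of Aim 1, with the 1-month difference and the trend as secondary. This conclusion depends on reading the Data Analysis Plan's ranking as governing the unranked mentions elsewhere. If a report of the trial claimed Aim 1 on the 1-month result alone, that would depart from the plan and should be challenged then.

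### The stated 80% power belongs to a log-scale ratio with a common CV of 0.65, but the plan describes mean differences and names no log analysis; the figure is not tied to the primary analysis.

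*Combined protocol and SAP*

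**What the plan says.** The Sample Size section opens in terms of differences in means: "Sample size calculations were performed based on detecting mean differences in PAP adherence at 1 and 3 months". It cites an earlier trial of motivational enhancement with "average PAP adherence of 264 minutes (SD: 174) as compared to average PAP adherence of 198 (SD: 168") in its control arm, and assumes a similar effect size. It then changes basis. It asks the reader to "assume that average adherence will be log-normally distributed with a coefficient of variation of 0.65, there will be 80% power". The target attached to that figure is "to detect an increase of 33% in the mean average nightly PAP adherence with 67 patients per group". One CV is given, with no derivation. The test is two-sided at 0.05. The 67 per group is raised to 83 for 10% non-participation and non-compliance in each group.

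The Data Analysis Plan says "Linear and non-linear mixed effect models will be used to compare groups for changes in PAP adherence (primary endpoint"); the same sentence covers the other outcomes. The contrasts are "mean differences primarily at 3 months and secondarily at 1 month", and "comparisons of mean differences at 1 and 3 months will each use a 0.05 significance level". Specific Aim 1 likewise frames the comparison as "on changes from baseline to 1 and 3 months in those with moderate to severe OSA with suboptimal PAP adherence". None of these sections names a log transformation, a ratio of geometric means, a rule for patients with no use, or a baseline covariate.

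**The concern.** The power calculation and the analysis description are not on the same footing. A log-normal assumption with a common CV gives the power of a test of log minutes, where the effect is a ratio. A mean difference, read in the ordinary way, is in minutes, where the effect is 66 and the variability is the cited SD. The two need not have the same power, and here they do not.

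The 80% is the only numeric power given for the primary endpoint. While the scale is open, a reader cannot tell which analysis the 80% describes, a null result cannot be judged against a known power, and the scale could be settled after the data are seen. The closing significance section also says that the trial should supply effect sizes for multicentre trials, so it matters whether that effect is a ratio or a number of minutes.

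**Working it through.** All power figures below are for a two-sided 0.05 two-sample t-test (noncentral t) with 67 evaluable per group, unless stated otherwise.

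**Inputs (Sample Size section).** Means 264 and 198 minutes; SDs 174 and 168; CV 0.65; 67 per group; 83 enrolled.

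**1. The plan's own figure.**
- Log SD = sqrt(ln(1 + 0.65²)) = 0.594.
- Log effect = ln(264/198) = ln 1.333 = 0.288. Standardised effect = 0.288/0.594 = 0.48.
- Power = 79.5% (80.1% by the normal approximation). The 80% reproduces.
- Enrolment = 67/0.9² = 82.7, so 83. This also reproduces.

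**2. Where CV 0.65 could come from.**
- Intervention arm: 174/264 = 0.66. Control arm: 168/198 = 0.85.
- Pooled SD = sqrt((174² + 168²)/2) = 171.0, and 171.0/264 = 0.65.
- So 0.65 is close to two figures built on the intervention mean, but it is applied to both arms and does not fit the control arm.

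**3. A mean difference in minutes, unadjusted.**

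| Assumed SDs | Pooled SD | Power for 66 min | Difference with 80% power |
|---|---|---|---|
| Cited: 174 and 168 | 171.0 | 60.2% | 83.4 min (83.4/198 = 42%) |
| CV 0.65 in both arms: 171.6 and 128.7 | 151.7 | 70.5% | 74.0 min (37%) |

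With the cited SDs the standardised effect is 66/171.0 = 0.39, against 0.48 in step 1, so the effect size powered for is larger than the cited one. The second row shows that the scale alone costs about 9 points (79.5 − 70.5), even if CV 0.65 is granted. Because minutes are skewed, a 40,000-replicate simulation of the t-test in minutes on log-normal data with the cited means and SDs was also run; it gave about 62%, so skewness does not explain the gap.

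**4. What baseline use could do (minutes, cited SDs).** The documents give no correlation between baseline and follow-up, so r is an assumption.

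| r | Baseline-adjusted: SD × sqrt(1 − r²) | Raw change, equal SDs: SD × sqrt(2(1 − r)) |
|---|---|---|
| 0.3 | 64% | 47% |
| 0.5 | 73% | 60% |
| 0.61 | 80% | 71% |

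**5. A log analysis of exactly the cited means and SDs, with no zero use.** Log SDs are 0.601 and 0.736. Geometric means, mean × exp(−log SD²/2), are 220.4 and 151.0 minutes. Their ratio is 1.46, and power is about 90%. This is for a ratio of 1.46, not the 1.33 that the plan states.

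**6. Sensitivity of a log analysis to zero use.** Zero has no logarithm, and the usual remedy is to add a constant. Simulation (20,000 replicates; CV 0.65; means 264 and 198 among users; unequal-variance t-test) with an assumed 5% of patients at zero in both arms gave power of about 25%, 42% and 52% for constants of 1, 10 and 30 minutes, against 65% in minutes. The 5% is an assumption; the documents give no share.

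**The case against.** The best defence is that the plan assumes log-normal adherence and a percentage increase, so a log analysis is the natural reading. With a common CV, a 33% increase in the mean is also a 33% increase in the geometric mean. The term mean differences does not itself say minutes, and non-linear models are allowed. This has some force, and it is why the 80% cannot be called an arithmetic error. But a distributional assumption made for power is not an analysis specification. The section that specifies the analysis names no log scale, and its non-linear models are listed jointly for adherence, PROs and yes/no barriers.

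A second objection is that an unadjusted two-sample comparison is planned nowhere, and that 60% is for 67 evaluable per group. That stands. If all 83 per group were evaluable with the full effect, the figure would be about 70%, and step 4 shows that use of baseline could raise or lower it.

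A reader might infer from the 60% that the trial is underpowered. The documents do not support that: with no baseline correlation, power for the planned mixed model cannot be computed, and plausible readings run from 47% to 90%. A reader might also infer that declaring a log analysis would make the 80% correct. That would hold only without zero users, with CV 0.65 in both arms and no adjustment. A constant added for zeros changes the estimand to a ratio for minutes plus the constant, and step 6 shows that a few zero users can cut power sharply.

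**Conclusion.** The point holds as a mismatch between the power statement and the analysis described. With the stated inputs, 80% is the power of an unadjusted log-scale comparison with ratio 1.33 and a CV of 0.65 in both arms; no such analysis is specified, and the CV is unsupported for the control arm. For the mean difference that the text describes, taken in minutes, unadjusted and with 67 evaluable per group, power for 66 minutes is about 60% with the cited SDs, or about 71% if CV 0.65 applied to both arms. These figures assume that the cited trial's means and SDs carry over. A shortfall in the trial itself is not shown. The defect should be fixed, and confidence is high that the scale is unstated and that the 80% does not carry over to minutes.

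**What to change.** Keep 83 per group.

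- **Data Analysis Plan.** State that the primary contrast is the between-arm difference in mean nightly PAP minutes at 3 months from the mixed model, with nights or patients without use counted as 0 minutes.
- **Sample Size.** Replace the claim of 80% power for a 33% increase with: *about 60% power for a 66-minute (33%) difference and 80% for about 83 minutes (42%), unadjusted, with 67 evaluable per group and the cited SDs.* Show any gain from baseline adjustment as an assumption, with the correlation used.

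If the sponsor does intend a log-scale primary analysis, it should say so, fix the zero-use rule in advance, give the basis of CV 0.65, and state power computed under that rule with an assumed share of zero users. Quoting 80% beside a log of minutes plus a constant would not be enough.

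The cost is wording and a less favourable stated power. No extra patients are proposed; the lower figure is disclosed, not bought back. For scale, 80% power for 66 minutes, unadjusted, would need 107 evaluable per group, or 107/0.9² = 132.1, about 132 enrolled.
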